9.3.6. Intraocular Pressure Tonometry

Intraocular pressure will be measured utilizing a Goldmann, Tono-Pen, or iCare tonometer (whichever is chosen, it must be used for the duration of the trial; no combination is permitted) and using the standard of care. If possible, the same calibrated instrument should be used for a given subject throughout the study.

9.3.7. Study Medication Tolerability Assessment

Subjects will be asked to rate the ocular tolerability of the medication according to the following 4-point scale:

0 = No discomfort

1 = Mild discomfort

2 = Moderate discomfort

3 = Severe discomfort

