4.1. Justification of Route, Dose, Regimen, and Treatment Period

Topical ocular administration of oxymetazoline hydrochloride at lower concentrations (0.01%, 0.025%) results in vasoconstriction and reduction of hyperemia but does not have the pharmacologic effect of improving the superior visual field or increasing the marginal reflex distance (MRD). This effect is present at a concentration of 0.1%, the concentration of RVL-1201, based on the results of the Phase 3 study, Study RVL-1201-201. The pilot study, Study RVL-1201-001, showed that RVL-1201 administered once daily (QD) and twice daily

(BID) was more effective at elevating the upper eyelid than Vehicle, but BID dosing did not result in increased upper eyelid elevation compared to QD dosing. The safety profile of RVL-1201 QD in both studies was satisfactory, with AEs that were mild, and did not require treatment. In the pilot study, slightly more subjects in the BID treatment group than in the QD treatment group reported AEs. These were deciding factors in going forward with QD dosing in the first Phase 3 study. The current Phase 3 study, Study RVL-1201-203 will evaluate the safety of 1 drop of RVL-1201 Ophthalmic Solution in each eye QD for 84 days. This dosing duration was chosen to evaluate the safety of longer-term dosing than the 42-day period evaluated in Study RVL-1201-201.

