6. INVESTIGATIONAL PLAN

6.1. Overall Study Design

This will be a Phase 3, randomized, multicenter, double-masked, placebo-controlled study to evaluate the extended safety of RVL-1201 Ophthalmic Solution compared to Vehicle (placebo) for the treatment of acquired ptosis. The study will be conducted over 84 days (12 weeks).

Eligible subjects will be randomized in a 2:1 ratio to one of the following 2 treatment arms and treated for 84 days:

- RVL-1201 Ophthalmic Solution 1 drop in each eye QD in the morning (N = 150)
- Vehicle (placebo) 1 drop in each eye QD in the morning (N = 75)

Both eyes will be treated and assessed.

Following screening evaluations at the Screening/Baseline visit (Day 1), a determination of eligibility will be made, and eligible subjects will be randomized and receive study medication.

Study medication, RVL-1201 or Vehicle (placebo), will be provided in identical-appearing unit-dose vials. The identity of the study medications will be masked to the subject, Investigator, study personnel responsible for ophthalmic evaluations, and Sponsor personnel.

Subjects (or their caregiver, if necessary) will administer study medication QD in the morning during the study period.

Safety follow-up visits will be conducted at Day 14 (Visit 2), Day 42 (Visit 3), and Day 84 (Visit 4).

[Table 2](#) provides a tabular summary of all scheduled visits and procedures to be performed during the clinical study.

Table 2: Schedule of Procedures (Study RVL-1201-203)

Assessment	Screening/Baseline Randomization Day 1	Day 14 (± 3 Days)	Day 42 (± 3 Days)	Day 84 (± 3 Days)	Early Discontinuation
Visit	1	2	3	4	
Informed consent	X				
Demographics/medical/ocular history	X				
Collect study medication materials		X	X	X	X
Urine pregnancy test ^a	X			X	X
Prior/concomitant medications	X	X	X	X	X
Adverse event assessment ^b	X	X	X	X	X
Tolerability assessment				X	X
Blood pressure/heart rate ^c	X	X	X	X	X
External digital photograph	X	X	X	X	X
Marginal reflex distance (OU) ^d	X				
Pupil diameter measurement (OU) ^d	X	X	X	X	X
Snellen visual acuity (OU) ^e	X	X	X	X	X
Slit lamp exam (OU)	X	X	X	X	X
Corneal fluorescein staining (OU)	X	X	X	X	X
Intraocular pressure tonometry (OU)	X		X	X	X
Dilated ophthalmoscopy/fundus exam (OU) ^f	X			X	X
Review inclusion/exclusion criteria / Randomize eligible participants	X				
Dispense/administer study medication ^g	X	X	X		

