10.3.5. Day 84 ± 3 (Visit 4): Final Treatment Visit

On Day 84 ± 3 , subjects will return all opened and unopened study medication materials and participate in final safety and tolerability assessments. Site personnel will conduct final study medication accountability procedures.

Visit 4 procedures include the following:

- Collect Box 3, containing all opened and unopened study medication materials (unit-dose vials and pouches), from the subject
- Urine pregnancy test (females of childbearing potential only)
- Concomitant medication review
- AE assessment
- Study medication tolerability assessment
- BP/HR
- Pupil diameter measurement (from external photograph)
- Snellen VA
- SLE
- CFS
- IOP
- Dilated ophthalmoscopy/fundus exam
- Final study medication accountability

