10.4. Early Discontinuation Assessment Procedures

If a study subject is discontinued from study medication before Day 84 (Visit 4) and after Day 1 (Visit 1), procedures performed will include the following:

- Collect all opened and unopened study medication materials (opened and unopened unit-dose vials and pouches) from the subject
- Urine pregnancy test (for females of childbearing potential only)
- Concomitant medication review
- AE assessment
- Study medication tolerability assessment (rating by subject)
- BP/HR (taken after 3 minutes at rest)
- Pupil diameter measurement (from external photograph)
- Snellen VA
- SLE
- CFS
- IOP
- Dilated ophthalmoscopy/fundus exam
- Study medication accountability

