11.5. Safety Endpoints

The safety of RVL-1201 compared to Vehicle will be evaluated by the following endpoints:

1. Comparison of ocular and non-ocular AEs by:
 - a. Frequency
 - b. Intensity
 - c. Relationship to treatment
 - d. Serious adverse events
 - e. Adverse events leading to withdrawal of study medication
2. Comparison of subjects with findings on the following measures:
 - a. Slit-lamp examination
 - b. Corneal fluorescein staining
 - c. Pupil diameter
 - d. Dilated ophthalmoscopy/fundus examination
 - e. Tonometry
 - f. Snellen VA (corrected)
 - g. Vital signs (BP/HR)
3. Comparison of tolerability as measured by the tolerability scale.

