6.2 Handling of Early Termination Visit Information

If a patient is terminated early from this study the early termination visit data will be analyzed at the closest scheduled visit. If the closest visit has valid data, the early termination data will be assigned to the next available visit.

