8.7 Tolerability Assessment

Tolerability assessments will be summarized in frequency tables based on the ordinal scale for each treatment group at the Day 84 assessment.

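### The tolerability scale is rated only at Day 84 or Early Discontinuation and has no reference period, so the scale itself cannot show change after Day 42, and some early-discontinuation ratings can miss the only planned table

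*Protocol*

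**What the plan says.** - **Endpoint.** Protocol 11.5 gives three numbered groups of safety endpoints. The third is "Comparison of tolerability as measured by the tolerability scale".
- **Item.** Protocol 9.3.7 reads "Subjects will be asked to rate the ocular tolerability of the medication according to the following 4-point scale", running from 0 (none) to 3 (severe). SAP 3.3.7 repeats it. Neither says whether the rating concerns the latest drop, recent days or the whole treatment period.
- **Timing.** In Table 2 (Protocol 6.1) the row "Tolerability assessment" is marked at Day 84 and Early Discontinuation only, and the schedule in SAP section 12 agrees. Protocol 10.3.5 lists "Study medication tolerability assessment" for Visit 4, and 10.4 lists it for early discontinuation. The lists for Visits 1, 2 and 3 (10.1, 10.3.1, 10.3.3) do not contain it.
- **Analysis.** SAP 8.7: "Tolerability assessments will be summarized in frequency tables based on the ordinal scale for each treatment group at the Day 84 assessment".
- **Early termination.** SAP 6.2: "If a patient is terminated early from this study the early termination visit data will be analyzed at the closest scheduled visit". Where that visit already holds valid data, the early data move on to the next visit.
- **Reason for 84 days.** Protocol 4.1: "This dosing duration was chosen to evaluate the safety of longer-term dosing than the 42-day period evaluated in Study RVL-1201-201".

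The two documents agree with each other on the schedule.

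**The concern.** The dosing period was lengthened to learn about use past 42 days, yet the one safety scale completed by the subject has no scheduled rating at Day 42 or earlier to set against the one at Day 84. Blood pressure and heart rate, pupil diameter, acuity, slit lamp and corneal staining are all repeated at Day 14 and Day 42, when the subject is at the site anyway.

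Two things are at stake. First, the scale cannot separate discomfort that builds up from discomfort that was there from the start, nor show whether the arms drift apart. The missing reference period makes this worse: a subject whose early stinging has gone could answer 0 or 2, depending on how the question is read. Second, the subjects most informative about tolerability are those who stop because of it, and their ratings may have no table to appear in.

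**Working it through.** The documents give no calculated sample size, power or dropout rate, and the analysis is descriptive, so there is no planned figure to reproduce. The check is a reading of the schedule, a walk through SAP 6.2, and an illustration of what added ratings would give.

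**1. Ratings available**

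| Visit | Scheduled rating (Table 2 and visit lists) | Table in SAP 8.7 |
|---|---|---|
| Day 1 | 0 | no |
| Day 14 | 0 | no |
| Day 42 | 0 | no |
| Day 84 | 1 | yes |
| Early Discontinuation | 1, for those who stop | not stated |

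The added period is 84 − 42 = 42 days. A change over it is the Day 84 rating minus the Day 42 rating and needs two ratings per subject. A completer has one, so neither the change nor its between-arm difference can be formed from the scale.

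**2. Where SAP 6.2 sends an early-discontinuation rating**

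Midpoints between visits are (14 + 42)/2 = Day 28 and (42 + 84)/2 = Day 63. The SAP does not say whether valid data are judged for the visit as a whole or for each assessment, so both readings are shown, assuming earlier visits were attended.

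| Example stop day | Closest visit | Visit-level reading | Assessment-level reading |
|---|---|---|---|
| 10 | Day 14 (4 days away; Day 1 is 9) | Day 14, no table | Day 14, no table |
| 20 | Day 14 (6; Day 42 is 22) | moves to Day 42, no table | Day 14, no table |
| 35 | Day 42 (7; Day 14 is 21) | Day 42, no table | Day 42, no table |
| 50 | Day 42 (8; Day 84 is 34) | moves to Day 84, tabulated | Day 42, no table |
| 70 | Day 84 (14; Day 42 is 28) | Day 84, tabulated | Day 84, tabulated |

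In these examples a rating given before Visit 3 falls outside the planned table on either reading. Between Visit 3 and Day 63 the reading decides.

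The number affected is unknown. On assumed losses of 10% or 20%, the arms fall from 150 and 75 to 135 and 68, or to 120 and 60. If every one of those subjects stopped before Visit 3 and was rated, the ratings outside the table would be at most 150 − 135 = 15 and 75 − 68 = 7, or 150 − 120 = 30 and 75 − 60 = 15. These are upper bounds on assumed rates.

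**3. What ratings at Day 42 would make estimable**

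Take the share *p* of subjects whose rating worsens from Day 42 to Day 84, assumed equal in both arms. The 95% half-width for the between-arm difference is 1.96 × √[p(1 − p)(1/n₁ + 1/n₂)]. For p = 10% with 150 and 75: 1.96 × √(0.09 × 0.02) = 8.3 percentage points.

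| Assumed p | 150 and 75 | 120 and 60 (assumed 20% loss) |
|---|---|---|
| 5% | 6.0 | 6.8 |
| 10% | 8.3 | 9.3 |
| 20% | 11.1 | 12.4 |
| 30% | 12.7 | 14.2 |

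The added ratings would describe the time course with moderate precision. Under the present schedule the quantity has no estimate.

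**The case against.** A reader might infer that the trial as a whole cannot show whether discomfort rises or falls. The documents do not support that. Protocol 9.4.1.1 has staff ask about problems at every clinic visit, with recall back to the previous one. Protocol 9.6 records onset and resolution dates and times, and grades mild and moderate severity in terms of discomfort. SAP 8.9 tabulates events by arm and lists them with onset date. Early discomfort that fades can therefore be captured as a dated event. The limits are that the questioning is open-ended, that it is not a repeated graded rating, and that the SAP plans no event summary by time period.

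The endpoint in Protocol 11.5 asks for a comparison of the arms, and a concurrent randomised comparison at Day 84 supplies one. No section sets a time-course objective for tolerability. Nor is a thin schedule peculiar to this item: tonometry is skipped at Day 14, and the fundus examination is not repeated before Day 84 except at early discontinuation. All of this stands, and it makes the matter a design preference rather than a fault.

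It would also be wrong to say that no rating before Day 42 can exist, since a subject who discontinues early may be rated then. That rating gives completers no time course, however, and it is the one SAP 6.2 can leave without a table. Finally, the eCRF may state a recall period, and the earlier study may have used the same scale. Neither can be settled from these documents.

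**Conclusion.** The point holds as a limit of the tolerability scale, not of the whole trial. Completers have one scheduled rating, 0 of the 2 follow-up visits before Day 84 carry the item, and no reference period is stated, so this endpoint cannot describe change over the added 42 days. Adverse event reports are the only source on timing, and an indirect one. The Day 84 between-arm comparison remains valid for subjects rated then. One caution applies: Protocol 8.5 encourages subjects who stop medication to keep attending, so some Day 84 ratings may come from subjects off drug, and the item does not say what such a rating covers.

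The gap between SAP 6.2 and SAP 8.7 is separate and should be closed whether or not visits are added. Its size depends on how many subjects stop before Visit 3, which the documents do not project.

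The conclusion assumes that the eCRF item is worded as in Protocol 9.3.7. This is a low-cost improvement; no planned figure is wrong and the documents do not contradict each other.

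**What to change.** 1. **Protocol.** Add the item at Visit 2 and Visit 3 in Table 2, 10.3.1 and 10.3.3. In 9.3.7, word it for a fixed period, for example the time since the preceding visit. Make the matching edits in SAP 3.3.7 and section 12.
2. **SAP 8.7.** Tabulate ratings by visit and arm, and cross-tabulate Day 42 against Day 84 within each arm.
3. **Early-discontinuation ratings.** Add a table of each subject's last available rating by arm, showing the day it was given. Label it as a summary of observed ratings, separate from the Day 84 table, so that it does not conflict with the rule against imputation. State in SAP 6.2 whether valid data are judged per visit or per assessment.

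The cost is a small amendment, one extra eCRF item at two visits already attended, and one or two more tables. If the visits are not added, the reference period and step 3 can still be adopted.

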9.4. Adverse and Serious Adverse Events

9.4.1. Definition of Adverse Events

9.4.1.1. Adverse Event (AE)

An AE is any untoward medical occurrence in a patient or clinical study subject administered a study medication (pharmaceutical/biological product) that does not necessarily have a causal relationship to this medication. An AE can therefore be any unfavorable and unintended sign (including abnormal laboratory findings), symptom, or disease temporally associated with the use of the study medication, whether or not related to the study medication. Study medication includes the investigational drug under evaluation and the comparator product or vehicle placebo that is given during any phase of the study.

Medical conditions/diseases present before starting the investigational treatment are only considered AEs if they worsen after starting the investigational treatment. Abnormal test results constitute AEs only if they induce clinical signs or symptoms, are considered clinically significant, or require therapy.

The occurrence of AEs should be sought by open-ended questioning of the subject at each visit during the study. At each clinic visit, study personnel should ask the following question: "Have you had any problems since your last visit?" AEs also may be detected when they are volunteered by the subject during or between visits or through study assessments.

9.4.1.2. Serious Adverse Event (SAE)

An SAE is any untoward medical occurrence that at any dose:

- Results in death,
- Is life-threatening,

Note: The term "life-threatening" refers to an event in which the subject was at risk of death at the time of the event; it does not refer to an event which hypothetically might have caused death if it were more severe.

- Results in persistent or significant disability/incapacity (excluding progression/outcome of the disease under study);
- Is a congenital anomaly/birth defect,
- Requires inpatient hospitalization or prolongation of existing hospitalization, or
- Is medically significant; i.e., defined as an event that jeopardizes the health of the subject or may require medical or surgical intervention to prevent one of the outcomes listed above.

Treatment on an outpatient emergency basis that does not result in hospital admission, or a hospitalization that is elective or is a preplanned treatment for a pre-existing condition that is unrelated to the indication under study and has not worsened since the start of the study, is not considered an SAE.

All SAEs that are ongoing at the time of completion or discontinuation from the study will be followed until stabilization or resolution of the event.

9.5. Relationship to Study Drug

The relationship of AEs to the study medication should be assessed by the Investigator using the definitions below.

Not suspected: The temporal relationship of the event to the study medication makes a causal relationship unlikely, or, other drugs, therapeutic interventions or underlying conditions provide a sufficient explanation for the observed event.

Suspected: The temporal relationship of the event to the study medication makes a causal relationship possible or other drugs, therapeutic interventions or underlying conditions do not provide a sufficient explanation for the observed event.

If there is any valid reason, even if undetermined, for suspecting a possible cause-and-effect relationship between the study medication and the occurrence of the AE, then the AE should be considered “suspected.”

If the relationship between the AE/SAE and the investigational product is determined by the Sponsor to be “suspected” the event will be considered to be related to the investigational product for the purposes of expedited regulatory reporting.

9.6. Recording Adverse Events

Adverse events spontaneously reported by the subject and/or in response to an open question from the study personnel or revealed by observation, regardless of severity or potential association with the study medication or study procedures, will be recorded in the eCRF.

Changes from baseline assessments that are part of the disease being studied will not necessarily be recorded as adverse events unless the Investigator deems them as such. Clinically significant changes in blood pressure and heart rate should be reported as AEs. All AEs that occur following consent and until the final study visit (Day 84, Visit 4) should be collected and recorded on the AE eCRF page. Serious adverse events will be followed until the event is resolved or stabilized.

The AE term should be reported in standard medical terminology when possible. For each AE, the Investigator will evaluate and report the following:

- Onset (date and time);
- Resolution (date and time);
- Severity grade (mild, moderate, severe);
- Relationship to study medication (not suspected, suspected);
- Action taken (none, study medication temporarily interrupted, study medication permanently discontinued; concomitant medication taken; hospitalization/prolonged hospitalization; other);
- Serious outcome (yes/no).

The severity grade should be determined by the Investigator using the definitions below.

- **Mild:** Discomfort noticed but no disruption of normal daily activity
- **Moderate:** Discomfort sufficient to cause interference with normal daily activity
- **Severe:** Incapacitating, with inability to perform normal activities

It is important to distinguish between serious and severe AEs. Severity is a measure of intensity (as defined directly above) whereas seriousness is defined by the criteria under [Section 9.4.1.2](#). An AE of severe intensity may not be considered serious.

Should a pregnancy occur, it must be reported and recorded on the pregnancy form. Pregnancy in itself is not regarded as an AE unless there is a suspicion that an investigational product may have interfered with the effectiveness of a contraceptive medication. The subject will be withdrawn from study medication and followed through conclusion of pregnancy. The outcome of all pregnancies (spontaneous miscarriage, elective termination, normal birth or congenital abnormality) must be followed up and documented.

9.7. Reporting Adverse Events

All SAEs (related and unrelated) will be recorded following consent and until the final study visit, Day 84 (Visit 4), following the end of treatment exposure. Any SAEs “suspected” to be related to the investigational product and discovered by the Investigator at any time after the study should be reported.

Any SAE that occurs must be reported to Oculos within 24 hours of its occurrence or within 24 hours of learning of its occurrence. Recurrent episodes, complications, or progression of the initial SAE must be reported to Oculos as follow-up to the original episode within 24 hours of the Investigator receiving the information. Information about all SAEs will be collected and recorded on the SAE form. All pertinent medical records and information collected during the treatment and follow-up of the subject should be maintained at the site with a copy emailed to [REDACTED]. The Investigator must assess the SAE relationship and complete the SAE form. Oculos/RevitaLid Inc. may request additional information. Follow-up information (e.g., discharge summary) will be retained in the subject’s chart and a copy will be emailed to [REDACTED]

In addition, all SAEs should be recorded on the Adverse Event eCRF page with the serious question marked “Yes”.

It is the Investigator’s responsibility to notify the approving IRB of any SAEs on a timely basis as instructed by the Sponsor following the Sponsor’s determination of causality.

All subjects who experience an SAE should be followed clinically and undergo the appropriate diagnostic evaluations until stabilization or resolution of the event.

RevitaLid will report all SAEs to the U.S. Food and Drug Administration (FDA) on the appropriate schedule depending if the event is drug related or not drug related, expected or unexpected (based on the available information in the [Investigator’s Brochure](#)).

Any death occurring during the study and follow up period should be reported as an SAE. For any death occurring through the end of the study, regardless of the degree of relationship to study medication, the SAE resulting in the death must be reported to Oculos. A death occurring after completion of the study does not require completion of the SAE form.

